Study Design:	
Phase 1 prospective non-randomised safety cohort study with all patients recruited from a single UK site (Oxford). The study has an open label design with all participants receiving ThermoDox® and FUS. The study will run in two parts. Part I is required to identify optimal FUS exposure parameters using real time thermometry data from an implanted thermometry device, such as a thermistor. Part II does not require implantation of thermometry device and is designed to more accurately reflect how the therapy would be implemented in clinical practice. All evaluable participants from both Part I and Part II will be included in the endpoint analysis.
 
Part I
 
For each participant, a single liver tumour will receive the intervention and follow-up imaging. The ability to achieve targeted release of doxorubicin from ThermoDox® at the tumour site will be determined using three tumour biopsies with corresponding peripheral blood samples taken during intervention and/or using a radiological method (MR-Spectroscopy).
 
Part II
 
For each participant, a single liver tumour will receive the intervention and follow-up imaging.. The optimal FUS exposure parameters determined in Part I will be selected for Part II interventions, accounting for differences in propagation path length identified in the Ultrasound Session. The ability to achieve targeted release of doxorubicin from ThermoDox® at the tumour site will be determined using the same methods as for Part I, with the exception of requiring only two tumour biopsies.
 
In the 30 days following intervention, both Part I and II participants will be followed up with a maximum of two CTs, two PET-CTs and three MRI/MR-Spectroscopy scans. There is however built in flexibility for the scans to be performed at different timepoints up to 60 days post intervention should the patient provide this optional consent and not have started another treatment. If available, other non-FUS control tumour(s) in the liver exposed to ThermoDox® alone will be selected as controls against which radiological response in the FUS-targeted tumour (target tumour) will be compared.
 
Detailed criteria for evaluation of efficacy and safety are described in subsequent sections.

Patient Numbers:	A maximum of 28 evaluable participants will be recruited to the study overall.

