Primary Endpoint:	A demonstrable two-fold increase in, or value exceeding 10µg/g of, the concentration of intra-tumoural doxorubicin at the treated tumour site following FUS-induced mild hyperthermia, in at least 50% of evaluable participants.
Secondary Endpoints:	
 Part I only: Achievement of the desired range of mild hyperthermia in the target tissue as monitored by the implanted thermometry device during FUS exposure

	
 2. Persistence of cell viability stain or percentage of cell or tissue necrosis under 30% following FUS exposure, as assessed by cytological or histological methods 3. Significant bone marrow suppression, deranged liver function and liver toxicity. 4. Adverse events up to 30 days post-intervention: 
 a. Deemed related to ThermoDox® b. Deemed related to FUS
Tertiary (Exploratory) Endpoints:	
Regarding doxorubicin released by optimal FUS exposure parameters:
 
 1. Combined analysis of relevant end points to establish most effective alternative analytical method(s) for quantifying drug release: 
 a. Released biopsy samples exhibiting averaged regions of nuclear or background fluorescence levels at least twice that of a suitable control, as assessed by fluorescence microscopy b. Liver MRI/MR-Spectroscopy indicating targeted delivery of doxorubicin to the tumour by demonstrating a statistically significant increase in the tumour:background ratio of signal intensity following intervention compared to baseline c. A significant decrease of in total doxorubicin plasma levels over time-matched clearance levels, following FUS-induced release 2. Radiological evidence of tumour response at timepoints up to 60 days post-intervention in the FUS-targeted tumour and control(s), as assessed by Principles of Choi and RECIST response evaluation using MRI and CT [11, 12] and SUV_{max} using PET-CT [13]

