¹⁰ During the Ultrasound Session feasibility of intervention is confirmed and a target tumour will be selected by ultrasound. Only one screening ultrasound is required.

¹¹ MRI includes the abdomen. Measurements made using the modified RECIST 1.1 criteria.

¹² Liver MRI includes the abdomen. The first Liver MRI/MR Spectroscopy following intervention can alternatively be performed on the same day as intervention, if intervention is in the morning. It should occur within 36 hours of the completion of intervention, and ideally within 24 hours where possible.

¹³ Liver pCT includes the abdomen. Measurements made using CHOI and the modified RECIST 1.1 criteria.

¹⁴ Three blood samples for pharmacokinetics in both Phases I and II (Pre-Treatment, Unreleased drug, Released drug).

¹⁵ Three biopsies in Part I (Pre-Treatment, Unreleased drug, Released drug), two biopsies in Part II (Released drug).

KEY DEFINITIONS

“Intervention” refers to attempted targeted release of ThermoDox® by mild hyperthermia using a focused ultrasound.

The “FUS-targeted tumour” or “target tumour” refers to the liver tumour treated with FUS following ThermoDox® delivery. This is in contrast to the RECIST definition, which defines target tumours as those measurable lesions which are followed through the patient’s treatment course.

A “non-FUS control tumour” refers to a liver tumour receiving ThermoDox® alone which has been selected for radiological follow-up and comparison with the target tumour.

The “desired range of mild hyperthermia” is used in the context of ThermoDox® release in this study and is defined as achieved bulk tissue temperature in the range of 41-47°C

“Optimal FUS exposure parameters” are defined as those combinations of settings on the HIFU device (power, duty cycle and transducer motion plan) which result in an adequate temperature rise to successfully release doxorubicin from the LTSls in the target tumour, without causing direct thermal tissue damage.

An “evaluable participant” is defined as a participant who has received FUS following delivery of ThermoDox® in Part I or II, and for whom it has been possible to evaluate the outcome of the intervention based on biopsy samples, or radiologically.

An “evaluable sample” is defined as a sample for which sufficient material was available for analysis and the analytical technique has provided quantifiable data.

ABBREVIATIONS

AE	Adverse Event
ADL	Activities of Daily Living
ADR	Adverse Drug Reaction

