3 OBJECTIVES AND ENDPOINTS

The objectives and endpoints for the study are detailed in the following tables. Only evaluable samples will be included in endpoint analysis. All endpoints will be evaluated at the end of Phase II.

The following qualifiers (*, †, ‡ and §) apply to Table 1, Table 2 and Table 3:

* In Part II the Unreleased biopsy is not performed and therefore the average value for all evaluable tumours receiving intervention in Part I is used as a comparison for the two-fold increase from Unreleased to Released biopsy.

† Duration refers to the completion of sample processing but not necessarily the sample analysis. The sample may be stored in a fixed or frozen state and analysed at some time period beyond the specified duration, for example to facilitate batch processing.

‡ Analytical method will only be performed where tissue mass allows. It is expected at most one technique can be performed in addition to the primary endpoint for a given sample. Where biopsy mass falls short, the primary endpoint will be prioritised.

§ Must be shown in at least 50% of evaluable participants.

Primary Objective	Primary Endpoint	How and when data is captured
To determine whether targeted release of doxorubicin from ThermoDox® ('drug') using mild hyperthermia generated non-invasively by focused ultrasound (FUS) is feasible in cancer patients	A demonstrable two-fold increase in*, or value exceeding 10µg/g of, the concentration of intra-tumoural doxorubicin at the treated tumour site following FUS-induced mild hyperthermia § Quantification of intra-tumoural drug release will be achieved by direct analysis of the intra-tumoural biopsy samples using standardised curve(s)	Analytical chemistry performed on a recorded mass of biopsy sample processed within 12 hours of intervention†

Table 1: Primary Objective and Endpoints for the TARDOX Study

Secondary Objectives	Secondary Endpoints	How and when data is captured
Part I only: To determine optimal FUS exposure parameters for a range of participant Body Mass Indices (BMIs) and tumour locations within the liver	Achievement of the desired range of mild hyperthermia in the target tissue as monitored by the implanted thermometry device during FUS exposure	Real-time thermometry monitoring during intervention

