6.1 Patient evaluability and replacement

Patients who are not evaluable for the primary endpoint will be replaced.

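### The denominator of the primary 50% rule is contradictory: radiology-only participants are both counted and replaced, and a Released core with unmeasurable drug can be read as non-evaluable

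*Protocol*

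**What the plan says.** The Protocol Synopsis sets the primary endpoint as a two-fold rise in intra-tumoural doxorubicin, or a value above 10 µg/g, "in at least 50% of evaluable participants". Section 3 repeats the 50% condition. Table 1 gives a single way to measure it: "Quantification of intra-tumoural drug release will be achieved by direct analysis of the intra-tumoural biopsy samples". MR-Spectroscopy appears in Table 3 as an exploratory endpoint, although the Study Design entry of the Synopsis allows release to be determined by biopsy, by MR-Spectroscopy or by both.

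Three further rules decide who is counted:

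- **Participant.** Key Definitions requires ThermoDox followed by FUS, and that it was possible to "evaluate the outcome of the intervention based on biopsy samples, or radiologically". Sections 2 and 17.1 take all evaluable participants of both Parts into the analysis, and section 16.1 caps their number at 28.
- **Sample.** Key Definitions calls a sample evaluable when "sufficient material was available for analysis and the analytical technique has provided quantifiable data". Section 3 adds: "Only evaluable samples will be included in endpoint analysis".
- **Replacement.** Section 6.1: "Patients who are not evaluable for the primary endpoint will be replaced". Section 16.1 applies this to non-evaluable participants and cites 6.1, as though the two terms meant the same.

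No text says how an adequate core with drug below the quantification limit is classified.

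**The concern.** The feasibility verdict is one observed proportion set against 50%, in at most 28 people, so a few participants moved into or out of the denominator can reverse it.

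First, the set used for the denominator admits participants by a route (radiology) that the endpoint does not recognise. The replacement rule treats the same people as unusable for that endpoint. Such participants are foreseeable: section 3 anticipates that biopsy mass may fall short, and section 5.2 schedules MRI/MR-Spectroscopy within 36 hours for everyone.

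Second, the sample rule has two separate conditions, enough material and quantifiable data. A core of adequate mass can fail on the second alone. If it fails because the drug was too low to quantify, the exclusion depends on the outcome itself.

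**Working it through.** **No figure to reproduce.** The Protocol states the maximum of 28 and the 50% rule but no null rate, target rate, significance level or power. The success rates and counts below are assumptions, and 28 is used because it is the cap.

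**Step 1. One participant, two rules.** Take a treated participant with a post-intervention MR-Spectroscopy scan and no usable Released core.

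| Followed text | Status |
|---|---|
| Key Definitions with sections 3, 16.1 and 17.1 | Evaluable by radiology; in the denominator; uses one of 28 places; cannot meet a biopsy criterion |
| Section 6.1 | Primary endpoint not evaluable; replaced. The text does not say whether the person also leaves the denominator |

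**Step 2. If r radiology-only participants stay among the 28.** Passing needs 14 successes from 28 − r biopsied participants, so the required rate is 14/(28 − r). The chance of passing is the exact binomial tail P(X ≥ 14) with n = 28 − r. At a true rate of 60%:

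| r | Required rate | P(pass) |
|---|---|---|
| 0 | 14/28 = 50.0% | 0.898 |
| 2 | 14/26 = 53.8% | 0.801 |
| 4 | 14/24 = 58.3% | 0.650 |
| 6 | 14/22 = 63.6% | 0.454 |
| 8 | 14/20 = 70.0% | 0.250 |

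**Step 3. If below-limit Released cores are treated as non-evaluable.** Suppose 28 treated participants have adequate cores and 12 succeed: 12/28 = 42.9%, a fail. If four of the 16 failures are below the limit and dropped, 12/24 = 50.0%, a pass. Replacement restores the number analysed but not the four failures. If a share q of treated participants is removed in this way, all of them failures, and then replaced, the analysed success rate is p/(1 − q). The tail P(X ≥ 14) with n = 28 becomes:

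| True p | q = 0 | q = 0.10 | q = 0.20 | q = 0.30 |
|---|---|---|---|---|
| 0.40 | 0.187 | 0.342 | 0.575 | 0.830 |
| 0.45 | 0.364 | 0.575 | 0.805 | 0.960 |

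The Protocol gives no quantification limit and no expected q. The table shows sensitivity, not a forecast.

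**Step 4. The comparator.** Section 3 compares Part II Released values with the Part I Unreleased average over evaluable tumours. Leaving out below-limit Unreleased cores removes the lowest values and raises that average. Two-fold then becomes harder to reach in Part II, so success goes down. A Part I participant whose Unreleased core is left out loses the fold criterion but can still succeed by exceeding 10 µg/g.

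**The case against.** The strongest reply has four parts.

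1. *The effects are alternatives.* A reader might infer that the plan both discards clear failures and retains radiology-only participants, so that both distortions act together. The text does not support that. Under Key Definitions, a participant with an unquantifiable core but a scan remains evaluable and stays in the denominator as a non-success. Under section 6.1 that participant is replaced, and so is a radiology-only one. This stands: it is one ambiguity with competing readings.
2. *Quantifiable data may only mean that the assay worked.* The Protocol never equates the phrase with drug above the quantification limit, and section 17.5 leaves analysis details to a SAP that is not shown. It is therefore not established that failures will be dropped. The literal reading remains open, however. Replacement is a Protocol rule, and if it operates during recruitment a rule in the SAP may come too late. If the literal reading is the intended one, a SAP that counted such a core as a failure would depart from section 3.
3. *The frequency is unknown.* ThermoDox is already circulating when the Unreleased core is taken, Part II allows up to two Released cores, and the primary assay has priority when tissue is short. Unmeasurable drug in an adequate Released core may be rare. This stands, so the values of q above are not evidence of size.
4. *Direction.* A reader might infer that the sample rule simply inflates the result, or that below-limit Unreleased cores remove Part I participants. Neither follows: section 3 excludes samples rather than people, the absolute criterion remains open, and a raised comparator lowers success.

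**Conclusion.** The contradiction over radiology-only participants is in the Protocol's current text and needs no inference: Key Definitions counts them, Table 1 gives them no way to succeed, and section 6.1 replaces them. The below-limit problem rests on the literal reading of the sample definition together with section 3. That reading is available but not compelled, and under section 6.1 it would select on the outcome.

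The net direction is undetermined. Keeping radiology-only participants works against the trial, dropping below-limit Released cores works in its favour, and dropping below-limit Unreleased cores works against it. Four participants out of 28 are enough to matter either way: a fail at 43% becomes a pass at 50%, or the bar among biopsied participants rises to 58% and the chance of passing at a true 60% falls from 0.90 to 0.65. These figures assume the maximum of 28 and invented counts. They show that the verdict can depend on which section is followed, not how often that will happen. Because this is the trial's only primary conclusion, the denominator should be settled before the analysis.

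**What to change.** Reconcile the Synopsis (Study Design), Key Definitions, section 3, section 6.1, section 16.1 and section 17.1 into one primary analysis set:

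- **Membership:** every participant who received ThermoDox and FUS and has an assayed Released biopsy of adequate mass. Remove the radiological route from the primary denominator, and keep radiology-only participants for the imaging endpoints.
- **Released result below the quantification limit:** evaluable, and a failure.
- **Unreleased result below the limit:** not dropped. Keep it in the Part I comparator under a prespecified convention, for example set to the limit.
- **Part I participant without an Unreleased core:** one rule that applies whatever the Released value. Otherwise a Released value of 12 µg/g would be counted as a success while 8 µg/g was set aside as unjudgeable, and inclusion would again depend on the outcome.
- **Replacement:** only for technical reasons, namely insufficient tissue or assay failure.

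The cost is a few lines of text and no new data. The stated success rate may come out slightly less favourable.

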1 INTRODUCTION

This proof of concept study proposes targeted delivery of a broad-spectrum cytotoxic agent (doxorubicin), via a specially formulated LTSL (ThermoDox®) activated by mild hyperthermia, to achieve enhanced intratumoural doxorubicin concentrations for the *same systemic dose*.

1.1 Background on Liver Metastases

1.1.1 Epidemiology

The development of distant spread (metastases) is a leading cause of death in patients with malignant solid tumours. Lung, breast and colorectal cancer are, in that order, the three most common cancers worldwide. These three cancer sites account for 40% of the world's total cases diagnosed, amounting to 4 million a year. They are also the leading cause of cancer death, resulting in almost 2.5 million deaths each year worldwide (International Agency for Research on Cancer: Fact Sheet, 2012).

The liver is one of the most common sites for metastatic disease. Liver metastases are diagnosed in 10–25% of patients at the time of resection of their primary colorectal tumour and, eventually, up to 70% of patients develop liver metastases [15, 16]. In patients with breast cancer, 15% of patients have liver metastasis at the time of diagnosis, and as many as 50% of patients with stage IV disease will develop metastases [17–21]. The most common sites for metastatic spread of breast cancer are the lung, bone and liver (50–71%) [22]. Approximately a third of patients with non-small cell lung cancer have liver metastases at the time of diagnosis [23].

In a significant proportion of patients, the liver is the only site of distant disease. In 30% of the patients with colorectal and breast cancer, the metastases are confined to the liver [15, 16, 24]. Studies have shown that the treatment of distant metastases improves survival. Life expectancy for patients with colorectal metastases without treatment is dismal and ranges from 5 to 9 months with a median survival after diagnosis of 6 months [1–3].

The presence of liver metastasis is an important prognostic factor in patients with lung cancer [25] with a reduction in the five-year survival rate from 36% to only 1% [25, 26]. Although recent advances in breast cancer treatment have significantly improved survival rates in recent years, metastatic breast cancer as a whole has a median survival time of two years which is largely unchanged [22]. Life expectancy of breast cancer patients with liver metastases improves from 3–6 months without treatment to 15–32 months with treatment [18, 20, 21, 27].

1.1.2 Treatment Modalities

Surgical resection remains the gold standard in the treatment of colorectal liver metastasis, as it is the only treatment shown to have long-term curative potential [4]. A large series of over one thousand patients followed up after liver resection for colorectal metastases demonstrated an operative mortality rate of 2.8% and a five-year survival of 37% for resections that involved a lobectomy or more [28]. However, only a minority (10–20%) of patients are surgical candidates due to either the cancer being too locally advanced, extra-hepatic, or being unfit for surgery due to co-morbidities [5]. Furthermore, the majority of patients undergoing liver resection develop new, non-resectable hepatic or extrahepatic metastases after hepatic resection [29, 30]. With the advent of neoadjuvant chemotherapy it is possible to convert some previously inoperable patients to the resectable group. A large trial of neoadjuvant systemic chemotherapy for colorectal liver metastasis looked at 330 patients with primarily unresectable liver disease from a cohort of 434 patients referred over a six year period. Of this group, 16% responded and went on to have liver resections with a comparable survival benefit to that of a primary liver resection (40% at 5 years). However, of the majority group with primarily unresectable tumours the vast majority (84%) remained inoperable [31].

Systemic chemotherapy remains the treatment of choice for patients with inoperable liver metastasis. Despite advances in systemic chemotherapy it remains a palliative treatment, as long-term survival is rare. In patients with liver metastasis from colorectal cancer, systemic chemotherapy with 5-fluorouracil (5-FU) has a response rate of only 20% with a median response duration of 6 months [32]. In the same patient group, combined chemotherapy regimens, such as 5-FU and leucovorin, have improved the median overall survival to approximately 12 months [33, 34] but with a trade-off of increased systemic toxicity.

Minimally invasive or non-invasive techniques in the treatment of patients with radiologically detectable and discrete metastatic liver disease are in demand, driven by surgical inoperability of the majority of liver metastases. Such non-invasive techniques are also in increasing demand among an ageing population. Ablative technologies are now becoming established and are showing encouraging outcomes for the treatment of metastatic liver disease. Such technologies are primarily being employed for palliation of patients with inoperable liver tumours who are unresponsive to chemotherapy. Modalities of ablative therapy include radiofrequency and microwave ablation, high intensity focused ultrasound (HIFU), laser and cryoablation. Overall, such techniques have the advantage over hepatic resection of shorter length of hospital stay and lower complication rates but the disadvantage of less proven survival benefits, although much clinical research activity is ongoing in this regard. Most of the current literature for ablative

therapies relates to treatment of hepatocellular carcinoma (HCC) rather than metastatic liver disease and to date there are no trials which compare outcomes between the various ablative technologies [35].

Trans-arterial techniques offer an alternative to ablative techniques. However no survival benefit has been shown in the treatment of colorectal metastases with embolization alone [36, 37] and several Phase III trials have failed to demonstrate a survival benefit in hepatic arterial chemotherapy over systemic chemotherapy [38]. Hepatic artery chemoembolization delivers a dual ischaemic and cytotoxic insult with theoretical benefits beyond either of the individual components of treatment [38]. However, multiple chemoembolization procedures are often required and reports of treatment response vary greatly among available studies. A previous study included 30 patients who received between one and three chemoembolization procedures using a combination of cytotoxic agents. Radiological response was seen in 63% of the cases but all responses were transient. Median survival was extended to 29 months after initial diagnosis of liver metastasis. Mild-to-moderate toxicity was seen and 'post-embolization syndrome' (fever, right upper quadrant pain, nausea and vomiting) was common [38].

Although targeted treatment of liver metastases with ablative or trans-arterial techniques allows localized, minimally invasive therapy without significant toxicity, the majority of patients with metastatic liver disease from malignant solid tumours are unsuitable for these therapies; thus palliative chemotherapy has been the mainstay of treatment. Nevertheless, the availability of these ablative modalities has stimulated interest in developing an additive or synergistic combination therapy for patients with metastatic disease using chemotherapy and ablation. The treatment of colorectal liver metastases with Radio-Frequency Ablation (RFA) provides palliation by extending life expectancy to a median survival of 36 months [39], representing a significant improvement over chemotherapy alone. However, such treatments must be radiologically amenable to accurate targeting of the tumour or tumours and thus only a limited number of metastatic tumours in the liver can be successfully treated by RFA.

